The programmatic intervention dose is lower than many health promotion interventions. The rationale is that 1) the intervention will be more impactful when delivered by a member of participant's social network,¹³⁸ and 2) non-programmatic health promoting activities and interactions are likely to occur within and between social networks (indirect intervention effect) throughout the study interval.¹³⁹ This approach highlights the potential advantages of social network interventions for scalability and sustainability.^{70,140}

The rationale for the mentorship and education component of the intervention arose from the success of this model in the Healthy Immigrant Families study, where the interventionists were not necessarily members of participant's social networks. For this application, mentorship has the potential to carry more influence through

delivery within social networks by respected peers. Peer mentoring has been shown to be effective in promotion of healthy eating and physical activity among groups with low socioeconomic position.^{141,142}

Treatment Fidelity & Measures

Treatment Fidelity

In the design and conduct of this study, we have incorporated recommendations from the Treatment Fidelity Workgroup.¹⁴³ We have recently described our process for assessing treatment fidelity for community-based behavior change interventions with immigrant groups in a CBPR framework.¹³⁶ The HPs will utilize a manual (phase 1) containing an outline/script for each session and a checklist of critical topics to be covered at each session. Study assistants, who were interventionists for the Healthy Immigrant Families study, will randomly observe 5% of sessions with the HPs. These study assistants have developed expertise as health behavior change interventionists through 250 hours of training followed by two years of intervention delivery.¹³⁶ They will be further trained in fidelity assessment for this study, thereby addressing the barrier of language concordance between interventionists and assessors. Bi-weekly meetings will be held with the HPs and study team to reinforce treatment fidelity, provide corrective feedback, and to conduct additional training if needed.

Measures

Data will be collected at 0 (baseline), 6, 12 (primary endpoint) and 24 months by trained study staff blinded to treatment condition. Participants will complete a survey and participate in physical measurements.

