Social network sub-groups are sufficiently discrete for randomization: Our social network data analysis determined that these communities were composed of enough discrete sub-groups for randomization. An example of this is that the Hispanic network had 144 unique sub-groups. When considering only sub-groups composed of five or more individuals, there were still 88 sub-groups identified using modularity calculations. This is a sufficient number of sub-networks for randomization, especially when considering the approximately equal number of Somali networks. Therefore, the high clustering observed in our preliminary data, as demonstrated by the high modularity of the networks, indicates that there are clearly distinct subgroups in the networks and that randomization via subgroups is feasible and appropriate for the study.

Sample size considerations

Stepped wedge cluster randomization trials typically have more statistical power than other cluster randomized designs.¹¹⁵ This is because each cluster is able to serve as its own control, accounting directly for the within cluster correlation of outcomes. In addition, the impact of intra-cluster correlation on power is typically smaller than on conventional cluster randomized trials.¹⁷¹ For the current study, we expect each HP to recruit 6 to 8 participants, so assume 7 per cluster and a substantial loss to follow up of 20% over 12 months. We assume a conservative intra-cluster correlation in outcomes of 0.10 to calculate the design effect DE_{sw} based on the formula:^{115,171}

$$DE_{sw} = \frac{1 + \rho(ktn + bn - 1)}{1 + \rho \left(\frac{1}{2}km + bn - 1 \right)} \cdot \frac{3(1 - \rho)}{2t \left(k - \frac{1}{k} \right)}$$

where $k = 2$ is the number of steps (including baseline), $b = 1$ is the number of measurements per subject in the baseline step, $t = 1$ is the number of measurements per subject at each step, and $n=7$ is the number of subjects per cluster. Assuming 80% follow up and equal

distribution across clusters, and a 80% power, we estimate the detectable standardized effects (SDs) for a range of numbers of enrolled HPs with a maximum probability of a Type II error of 0.05.

SD	HPs	N total
0.1	478	1673
0.2	120	420

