0.3 53 187 For the primary endpoints, a third standard deviation (0.3SD) difference between groups will be considered clinically meaningful.¹⁷² On the basis of the previous Healthy Immigrant Families study, we will assume a 0.1 standard deviation change in the control group ("contamination") so this represents a 0.4SD change in the intervention group. Therefore, the study will accrue 54 clusters (27 per group) with approximately seven participants in each cluster, for a total sample size of approximately 378 network participants.

Data Analysis

All analyses will be appropriate for stepped wedge trials. In the direct effects model, the co-primary endpoints will be changes in BMI and waist circumference from baseline to month 12 and the 12-month change in the Ajzen TPB, the common outcome for C2DREAM. We will use mixed effects regression models to adjust for correlations within social network clusters and over time.¹¹⁴ Models will include indicators for intervention status, step, and their interaction. Covariates indicated above including demographics (e.g., sex, years since arrival to the US) and social covariates will be included in profile analysis models to assess the sensitivity of the primary analysis conditional on these potential concomitant (mediating) influences. All secondary endpoints will be analyzed using the same methods as used for the primary endpoints.

Missing data will be handled in several ways using an extensive library of macro procedures designed specifically for such tasks by the Mayo Clinic Division of Biostatistics.¹⁷³ Simple imputation methods such as minimum, average, or maximum values carried forward will be followed by multiple imputation methods to assess the robustness of the study results in the presence of the missing data. All models will be assessed for goodness of fit, with effects reported with confidence intervals. All hypothesis tests will use $\alpha = 0.05$ to determine significance.

Bibliography

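### The plan does not say which missing-data handling gives the primary month-12 result, and it lists carry-forward fills that would distort that result if relied on

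*Combined protocol and SAP*

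**What the plan says.** The missing-data plan is two sentences in the Data Analysis section. The first is general: "Missing data will be handled in several ways using an extensive library of macro procedures". The second gives the order of methods: "Simple imputation methods such as minimum, average, or maximum values carried forward will be followed by multiple imputation methods", and it ends by stating a purpose, "multiple imputation methods to assess the robustness of the study results in the presence of the missing data".

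The same section defines the endpoints, "the co-primary endpoints will be changes in BMI and waist circumference from baseline to month 12" (with a psychosocial measure alongside), and the model: "We will use mixed effects regression models to adjust for correlations within social network clusters and over time". Measures gives the visits: "Data will be collected at 0 (baseline), 6, 12 (primary endpoint) and 24 months". Sample size considerations expects "a substantial loss to follow up of 20% over 12 months".

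Five things are not stated:
- which handling produces the primary result;
- whether the mixed model is fitted to observed values without imputation;
- whose minimum, average or maximum is carried forward (the person's own is the usual meaning);
- what missingness assumption applies;
- what the imputation model contains (arm, cluster, month-6 value).

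**The concern.** A fill carried to month 12 is a baseline value, a month-6 value or a mixture of the two, analysed as if it had been observed. Figure 1 and the Interventions section put the content sessions in the first six months and maintenance sessions, without new content, in the next six. There is no reason to expect either earlier value to equal the month-12 value.

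With 378 planned participants and 20% loss, about 378 × 0.20 = 76 month-12 values would be fills. As written, the analyst could report a carry-forward result as primary with multiple imputation as the check, or treat the whole sequence as a robustness exercise. Under either reading, carry-forward results could be used to support the conclusion.

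**Working it through.** The missing-data text states no figure to reproduce, so the check asks what the three rules do to a month-12 difference.

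**Inputs from the documents.** 54 clusters of 7, intra-cluster correlation 0.10, 20% loss (Sample size considerations). Weight goal 3% (Specific Aims); pilot baseline weight 91.6 kg (Table 2), so 0.03 × 91.6 = 2.75 kg. The pilot change was 91.6 − 89.7 = 1.9 kg with N = 39 and p < 0.0001, so the SD of change is at most 1.9 × √39 / 4.35 = 2.73 kg.

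**Assumptions.** SD of change 2.7 kg at month 6 (the bound above is from week 12) and 4 kg at month 12; correlation 0.7; no mean change in controls; loss at random; each person's own value carried; cluster means compared by t-test as a stand-in for the mixed model.

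**Mean of a fill, as change from baseline, when month 6 was seen.** The average rule gives half the month-6 change. The minimum rule gives E[min(0, X)] = μΦ(−μ/σ) − σφ(μ/σ), and the maximum rule gives μ minus that.
- Control (μ = 0, σ = 2.7): minimum −1.08, maximum +1.08.
- Intervention (μ = −2.75): minimum −2.97, maximum +0.22.
- Difference between arms among the filled: minimum −1.89, average −1.375, maximum −0.86 kg.

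If month 6 is also missing, every rule carries baseline and the difference is 0. With a fraction f of dropouts seen at month 6, the estimate is 0.8 × true effect + 0.2 × f × (difference among the filled).

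**Persisting effect, true −2.75 kg, equal loss**

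| f | minimum | average | maximum | shrinkage |
|---|---|---|---|---|
| 1 | −2.58 | −2.48 | −2.37 | 6-14% |
| 0.5 | −2.39 | −2.34 | −2.29 | 13-17% |
| 0 | −2.20 | −2.20 | −2.20 | 20% |

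Simulation at f = 1 (2,500 runs) gave −2.58, −2.47 and −2.36. A second simulation (3,000 runs) used the plan's own effect: −0.4 SD against −0.1 SD, a true difference of −0.300. Shrinkage ran from 9% (minimum, f = 1) to 21% (f = 0); the last is 20% by arithmetic, and the rest is simulation noise. At f = 0.5 the three rules gave −0.258, −0.254 and −0.251 with 92.4-93.4% coverage. Multiple imputation gave −0.300 with 94.5%.

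**No true effect, 30% against 10% loss, all dropouts seen at month 6.** The minimum rule is biased by (0.30 − 0.10) × (−1.08) = −0.22 kg and the maximum rule by +0.22 kg. With a standard error near 0.47, a shift of 0.22 predicts rejection in about 7%. Simulations gave 7.8-8.3% (minimum) and 7.0-7.8% (maximum). With 25% against 15% loss and a common −0.4 SD change, the maximum rule rejected in 8.1%. With no effect, no change over time and equal loss, bias is about zero and rejection about 5%.

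**Standard error.** Observed data: √{(2/27) × [0.10 × 16 + 0.90 × 16 / 5.6]} = 0.56 kg, where 5.6 = 7 × 0.8. Carry-forward gave 0.46-0.48. From unrounded values, 1 − 0.476/0.56 = 15% and 1 − 0.456/0.56 = 19%. On the SD scale, carry-forward gave 0.115-0.117 against 0.137 for multiple imputation (15-16% lower; 11-20% as f goes from 1 to 0).

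**Stress case.** A 2.75 kg month-6 effect is 2.75/2.7, or about 1 SD. If it is wholly lost by month 12 and f = 1, the false effects are 0.2 × (−1.89, −1.375, −0.86) = −0.38, −0.28 and −0.17 kg. Simulated rejection was about 11%, 9% and 6%, against 5.0% with observed data.

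**The case against.** **Carry-forward is only a robustness exercise.** The sentence does end with that purpose, and a mixed model is named separately that can use incomplete visits without imputation. A reader might infer that carry-forward is the chosen primary method. The documents do not say so; it is one of two readings. What remains is that neither reading is excluded.

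**The standard error is not wrong.** A reader might infer that carry-forward understates its own uncertainty. It does not: in the stress case the model standard errors (0.476, 0.461, 0.456) match the estimators' sampling SDs (0.477, 0.463, 0.460). The harm is bias combined with an interval narrower than a valid month-12 analysis gives.

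**The high false-positive rate is contrived.** This stands. The 11% figure needs an effect of about 1 SD, against the plan's 0.3 SD, wholly lost despite twelve maintenance sessions, with every dropout seen at month 6. If half of dropouts also miss month 6, rejection is about 5-7%. With a 0.3 SD month-6 effect wholly lost, it is about 5-6%.

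**Minimum and maximum bound the answer.** Sometimes they do. If half of a 2.75 kg effect is regained (true −1.375) and all dropouts were seen at month 6, the rules give −1.48, −1.38 and −1.27. But with a persisting effect all three fall short of −2.75, and in the stress case all three lie on the same side of zero. Agreement among them is therefore not evidence of robustness.

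**Conclusion.** The concern holds in a conditional form. The plan leaves the primary missing-data handling open and lists carry-forward fills ahead of an unspecified multiple imputation. If a carry-forward result were primary or used as evidence of robustness:
- a persisting effect would shrink by roughly 6-21% under equal 20% loss, depending mainly on how many dropouts also miss month 6;
- under the unequal-loss scenarios examined, with no true effect, the minimum or maximum rule would reject in about 7-8% of runs;
- the standard error would be about 15-19% below that of an observed-data or multiple-imputation analysis.

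Bias is not inevitable: it is about zero when loss is equal and there is no effect and no change over time. Differential loss is a fair scenario to examine, because the rationale for the design itself raises it as a possible concern, although it also reports high retention in both groups of the earlier trial. The sizes rest on the assumed SDs, the 0.7 correlation, the dropout patterns and the cluster-mean analysis.

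**What to change.** State in the Data Analysis section that the primary analysis is the planned mixed model, fitted by likelihood to all observed values at months 0, 6 and 12, with cluster and participant random effects and no imputation, and state the missingness assumption.

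Make multiple imputation the first sensitivity analysis: done by arm, respecting clusters and including the month-6 value. Drop the carry-forward fills, or label them supplementary and not used for the conclusion. A delta-adjusted analysis, in which imputed intervention values are made progressively worse, is an optional addition.

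The cost is SAP wording and a little more analysis. No extra data are needed.
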